7.2 Randomization

The treatment arm is determined by random selection using an MS Excel spreadsheet on the night of the study. The spreadsheet generates a number between 1 and 10,000. The TPAP therapy will be the starting therapy when an even number is generated by the spreadsheet; the CPAP therapy will be the starting therapy when an odd number is generated.

7.3 Populations for Analyses

For the purposes of analysis, the following analysis sets are defined:

Set	Description
Randomized	All participants who were randomized.
Modified Intent to Treat (mITT) Set	The mITT set comprises all participants who are randomized, undergo at least 1 h in any study arm, and have at least 1 measurement on the primary endpoint. Participants will be analyzed for equivalence.
Safety Set	The Safety Set consists of all participants who are randomized and undergo at least 1 h in any study arm.
Per Protocol (PP) Set	The PP Population consists of all participants without any major protocol violations and have considered to be evaluable for study analysis.

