4.1 Overall Design

The TheraPAP Equivalence Study is a randomized, controlled, crossover study in participants with OSA. Pre-screening is conducted to establish potential eligibility with a previous sleep study showing an AHI>10 events/hour, and a minimum of two months of adherent CPAP usage (defined as averaging > 5 hours/night). Eligible participants will undergo a split-night, in-laboratory polysomnogram (PSG) on CPAP and TPAP (3.5 hours for each treatment arm). The sequence of periods for each participant will be assigned in random order, although all participants will start on CPAP until asleep to blind them to the therapy arm. Therapeutic CPAP level will be defined based on each individual's pressure P95/P90 + 1 cmH₂O from the APAP

⁴ 10 minute per condition must be present for the endpoint to be considered.

⁵ 10 minute per condition must be present for the endpoint to be considered.

⁶ Although there will not be any direct treatment vs. control comparison here, we will assume that CPAP is safe and that any abnormal value recorded in the next morning compared to the evening before the polysomnography is due to treatment with TPAP.

device being used in the home over the previous two months. The drop in inspiratory PAP during the TPAP intervention arm will be based on the above P95/P90 according to Table 1.

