4.2.3 In-laboratory overnight PSG

The PSG will be conducted with a split-night design, i.e., approximately 3.5 hours on CPAP and 3.5 hours on TPAP, in random order. The switch between CPAP and TPAP will be operated through the interface screen on the TPAP device. During testing, no expiratory pressure relief will be used during CPAP regardless of such use during normal therapy at home. All patients will be asked to bring in the mask they normally use at night so that it can be used in the study, and the patients will be tested using two 1.8 m lengths of 22 mm tubing to prevent cross contamination. A commercial humidifier will be used to provide humidification since humidification is not supplied with the TheraPAP prototype.

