5.5 Measures to Minimize Bias

Each participant will begin the study in one of the treatment arms, (either CPAP or TPAP). The starting treatment arm is determined by a random number generator, as described in Section 7.2. All participants will start on CPAP until they fall asleep, then they will be switched to their designated therapy arm.

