5.7 Discontinuation of Study Treatment

If a clinically significant finding is identified, the Investigator or qualified designee will determine if the participant can continue in the study and if any change in participant management is needed. Any new clinically relevant finding should be reported as an adverse event (AE).

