5.8 Stopping Criteria

5.8.1 Individual Participant Stopping Criteria

Participants reporting any SAE considered possibly related or related to study device will be withdrawn from the study.

Any other AE that in the judgment of the Investigator necessitates the participant stopping to protect participant safety, will result in early withdrawal from the study.

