6.2 Safety Assessments

Planned time points for all safety assessments are provided in the SoA.

Safety assessments will include measurement of vital signs, monitoring and recording of AEs, SAEs, and recording of study or treatment discontinuations. Effects on OSA and sleep parameters (e.g., sleep time and sleep stages) will also be monitored by PSG.

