6.3.1 Time Period and Frequency for Collecting AE and SAE Information

All AEs and SAEs will be collected from randomization until the end of the study at the timepoints specified in the SoA.

All SAEs will be recorded and reported to the Sponsor or designee within 24 hours, as indicated in

Appendix . The Investigator will submit any updated SAE data to the Sponsor within 24 hours of it being available.

Investigators are not obligated to actively seek AEs or SAEs after the conclusion of study participation. However, if the Investigator learns of any SAE, including a death, at any time after a participant has been discharged from the study, and he/she considers the event to be reasonably related to the study or study participation, the Investigator must promptly notify the Sponsor.

The method of recording, evaluating, and assessing causality of AEs and SAEs and the procedures for completing and transmitting SAE reports are provided in

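### The Safety Set's one-hour minimum leaves out a participant who withdraws completely for an adverse event before reaching an hour in either mode

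*Combined protocol and SAP*

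**What the plan says.** Section 7.3 defines the safety population: "The Safety Set consists of all participants who are randomized and undergo at least 1 h in any study arm". The same section defines a Randomized set, but assigns no safety analysis to it.

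Other sections treat safety as starting earlier than the first hour:

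- Section 6.3.1: "All AEs and SAEs will be collected from randomization until the end of the study", at the times in the Schedule of Activities.
- Section 5.8.1: an AE that in the Investigator's judgment "necessitates the participant stopping to protect participant safety, will result in early withdrawal from the study". No minimum time on the device is attached. Section 5.9 lists an AE among the withdrawal reasons to be recorded.
- Section 6.2: "Safety assessments will include measurement of vital signs, monitoring and recording of AEs, SAEs, and recording of study or treatment discontinuations".

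Two further provisions determine who is affected. Section 5.7 says that when a clinically significant finding arises, "the Investigator or qualified designee will determine if the participant can continue in the study". Section 5.5 says: "All participants will start on CPAP until they fall asleep, then they will be switched to their designated therapy arm". The planned exposure in section 4.2.3 is "approximately 3.5 hours on CPAP and 3.5 hours on TPAP, in random order".

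On attribution, footnote 6 (attached to the safety endpoints and printed under section 4.1) says there will be no direct comparison of treatment with control. It continues that "we will assume that CPAP is safe and that any abnormal value recorded in the next morning", relative to the previous evening, results from TPAP. Appendix 2 classes abnormal safety values that the Investigator judges clinically significant as AEs. It requires the Investigator to assess causality for each one, with alternative causes considered.

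**The concern.** A safety population should not depend on how well the participant tolerated the treatment. Here it can. Someone who has an AE soon after the device starts, and leaves the study because of it, provides two items that the plan treats as safety information: the event and the discontinuation. Because the participant stopped before an hour, both fall outside the set from which safety would be summarized. Among participants with AEs, the rule removes those whose event ended participation soonest.

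At stake is the completeness of the safety summary in a one-night study of 52 people on a prototype device, where spontaneous AEs are the only listed safety endpoint. A summary built on this set could report no AEs when one participant had in fact withdrawn for one.

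**Working it through.** The plan computes no safety figure, so there is none to reproduce. The check compares the texts and then gives one illustration.

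**Step 1. Apply the definition to the possible cases.**

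| Case | AE within the collection window of 6.3.1? | In the Safety Set of 7.3? |
|---|---|---|
| AE, Investigator lets the participant continue, at least 1 h reached in one mode | Yes | Yes |
| AE on TPAP, TPAP stopped early, at least 1 h on CPAP | Yes | Yes |
| AE, complete withdrawal with less than 1 h in each mode | Yes | No |
| AE soon after the switch to TPAP, complete withdrawal, more than 1 h of CPAP lead-in before sleep | Yes | Not determined by the text |
| AE after randomization but before the device starts, participant leaves | Yes | No |

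The third row is the gap. The fourth row arises because nothing says whether the lead-in counts as time in a study arm, so two analysts could build different sets from the same data. The fifth row would stay outside even a set based on any device exposure and needs its own listing. Section 6.3.1 covers it, although the Schedule of Activities marks AE monitoring only for the overnight and morning columns.

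**Step 2. Look for text that closes the gap.** The Randomized set would contain the participant in the third row, but no safety summary is assigned to it. The mITT set uses the same hour. A minimum recording time has an evident purpose there, because AHI is measured over recorded sleep. No purpose is given for it in the Safety Set.

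**Step 3. Illustration of one omission.** Inputs: N = 52 (section 7.1). Assumptions, not from the documents: all 52 are randomized and start the device, exactly one withdraws for an AE before 1 h, everyone else reaches 1 h, and x of the others have an AE. With any exposure counted, the rate is (x + 1)/52. With the set as written, it is x/51. For r participants with AEs out of n, the exact one-sided 95% upper limit is the 0.95 quantile of the Beta(r + 1, n − r) distribution. For 0/51 this reduces to 1 − 0.05^(1/51) = 5.70%.

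| Others with an AE (x) | Any exposure | Upper limit | As written | Upper limit |
|---|---|---|---|---|
| 0 | 1/52 = 1.92% | 8.80% | 0/51 = 0% | 5.70% |
| 2 | 3/52 = 5.77% | 14.24% | 2/51 = 3.92% | 11.83% |
| 5 | 6/52 = 11.54% | 21.51% | 5/51 = 9.80% | 19.52% |

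Under these assumptions the rate falls by 1.92, 1.85 and 1.73 points, and the limit by 3.10, 2.41 and 1.99 points. The plan specifies no AE rate and no confidence limit. The table shows what one omission would do to such a summary, not how likely an omission is.

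**Step 4. Footnote 6 beside Appendix 2.** For an abnormal value that is not clinically significant, Appendix 2 does not create an AE, so the two texts do not meet. For a clinically significant value, footnote 6 points to TPAP while Appendix 2 calls for individual judgment. The footnote may be a conservative convention for reading the endpoint across the study, while Appendix 2 governs single cases. The two can then coexist, but the document does not say that this is the intention.

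**The case against.** The strongest case on the other side is that the gap is mostly theoretical and nothing is lost from safety oversight. Participants are established PAP users who begin on CPAP, and the protocol describes the study risk as minimal. Complete withdrawal for an AE before an hour in either mode should be rare. If it occurs, the event is recorded, the reason for withdrawal is recorded, an ongoing AE is followed up, and a serious event goes to the sponsor within 24 hours. No AE rate, limit or safety threshold is planned, so no stated decision would change.

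All of that stands, and it limits the size of the point. It does not remove the gap: collecting an event is not the same as including it in the safety summary, and the definition as written excludes it.

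A reader might infer three stronger things that the documents do not support:

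- *That early AEs go unrecorded.* They do not. The gap is in the analysis set only.
- *That anyone who stops TPAP early for an AE is dropped.* An hour on CPAP keeps that person in.
- *That footnote 6 contradicts Appendix 2 or hides harm.* The footnote discloses its assumption, counts against TPAP, disclaims a treatment comparison and can be read as a study-level convention. Its wording also presupposes that TPAP was given, so it does not clearly reach a participant who never received it. What remains is an unexplained relation between two rules, not a demonstrated conflict.

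**Conclusion.** The point holds for the Safety Set. As written, the definition leaves out a complete AE withdrawal before an hour in either mode, and it does so because of the outcome being summarized. This rests on reading section 7.3 literally and on the absence of any text assigning safety summaries to another set. How often the case would arise cannot be estimated from the documents. If it arose once, the effect on a crude AE proportion would be just under two percentage points, and with no other AEs the summary would change from one event to none. The primary AHI analysis is untouched.

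Footnote 6 is a minor matter of clarification and does not add to the weight of the main point.

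**What to change.** In section 7.3, define the Safety Set as all randomized participants with any exposure to the study device, stating that the CPAP lead-in counts and dropping the one-hour minimum. Add that any AE between randomization and device start is listed separately.

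In footnote 6, add a sentence stating how its assumption relates to the Investigator's causality assessment in Appendix 2 for clinically significant values, so that the two texts are reconciled.

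The cost is a change of wording. No procedure, visit or participant is added. The AE count may look slightly less favourable, and the denominator may include a few people with very short exposure, which can be shown by reporting exposure time alongside. The mITT definition need not change for this purpose.

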7.4 Interim Analyses

No interim analysis is planned.

8 Supporting Documentation and Operational Considerations

- Appendix 1: Regulatory, Ethical, and Study Oversight Considerations
- Appendix 2: Adverse Events: Definitions and Procedures for Recording, Evaluating, Follow-up, and Reporting
- Appendix 3: List of Abbreviations

Appendix 1: Regulatory, Ethical, and Study Oversight Considerations

1. Regulatory and Ethical Considerations

This study will be conducted in accordance with the protocol and with:

- Consensus ethical principles derived from international guidelines including the Declaration of Helsinki and Council for International Organizations of Medical Sciences International Ethical Guidelines.
- Applicable International Conference on Harmonization (ICH) Good Clinical Practice (GCP) Guidelines.
- Applicable laws and regulations.

The protocol, protocol amendments, ICF, and other relevant documents (e.g., advertisements) must be submitted to an IRB by the Investigator and reviewed and approved by the IRB before the study is initiated.

Any amendments to the protocol will require IRB approval before implementation of changes made to the study design, except for changes necessary to eliminate an immediate hazard to study participants.

The Investigator will be responsible for the following:

- Providing written summaries of the status of the study to the IRB annually or more frequently in accordance with the requirements, policies, and procedures established by the IRB.
- Notifying the IRB of SAE or other significant safety findings as required by IRB procedures.
- Overall conduct of the study at the site and adherence to requirements of 21 Code of Federal Regulations (CFR), ICH GCP guidelines, the IRB guidelines, and all other applicable local regulations.

2 Financial Disclosure

Investigators will provide the Sponsor with sufficient, accurate information in accordance with local regulations to allow the Sponsor to submit complete and accurate financial certification or disclosure statements to the appropriate regulatory authorities. Investigators are responsible for providing information on financial interests during the course of the study and for 1 year after completion of the study.

3 Informed Consent Process

The Investigator or his/her representative will explain the nature of the study to the participant or his/her legally authorized representative and answer all questions regarding the study.

Participants must be informed that their participation is voluntary. Participants will be required to sign a statement of informed consent that meets the requirements of 21 CFR 50, local regulations, ICH guidelines, Health Insurance Portability and Accountability Act requirements, where applicable, and the IRB.

The medical record must include a statement that written informed consent was obtained before the participant was enrolled in the study and the date the written consent was obtained. The authorized person obtaining the informed consent must also sign the ICF.

Participants must consent to the most current version of the ICF(s) during their participation in the study.

A copy of the signed ICF(s) must be provided to the participant.

If a protocol amendment is required, the ICF may need to be revised to reflect the changes to the protocol. If the ICF is revised, it must be reviewed and approved by the appropriate IRB and signed by all participants subsequently enrolled in the study.

4 Data Protection

Participants will be assigned a unique identifier by the study site. Any participant records or datasets that are transferred to the Sponsor will contain the identifier only; participant names or any information which would make the participant identifiable will not be transferred.

The participant must be informed that his/her personal study-related data will be used by the Sponsor in accordance with local data protection law. The level of disclosure must also be explained to the participant.

The participant must be informed that his/her medical records may be examined by Clinical Quality Assurance auditors or other authorized personnel appointed by the Sponsor, by appropriate IRB members, and by inspectors from regulatory authorities.

5 Data Quality Assurance

All participant data relating to the study will be recorded on electronic reports and spreadsheets. Any study data will be de-identified. The Investigator is responsible for verifying that data entries are accurate and correct by physically or electronically signing the study records.

The Investigator must maintain accurate documentation (source data) that supports the information entered in the study records.

The Investigator must permit study-related monitoring, audits, IRB review, and regulatory agency inspections and provide direct access to source data documents.

The Sponsor or designee is responsible for the data management of this study including quality checking of the data.

Records and documents, including signed ICF, pertaining to the conduct of this study must be retained by the Investigator for 5 years after study completion unless local regulations or institutional policies require a longer retention period. No records may be destroyed during the retention period without the written approval of the Sponsor. No records may be transferred to another location or party without written notification to the Sponsor.

All data generated by the site personnel will be captured and stored in an internal password-protected system.

6 Source Documents

Source documents provide evidence for the existence of the participant and substantiate the integrity of the data collected. Source documents are filed at the site.

7 Publication Policy

The Sponsor will generally support publication, reserving the right to review prior to submission.

Authorship will be determined by mutual agreement and in line with the International Committee of Medical Journal Editors' authorship requirements.

A summary of the study results will also be posted in a publicly accessible database (e.g., www.ClinTrials.gov).

8 Protocol Approval and Amendment

Before the start of the study, the study protocol and/or other relevant documents will be approved by the IRB/Competent Authorities, in accordance with local legal requirements. The Sponsor must ensure that all ethical and legal requirements have been met before the first participant is enrolled in the study.

This protocol is to be followed exactly. To alter the protocol, amendments must be written, receive approval from the appropriate personnel, and receive IRB/Competent Authority approval prior to implementation (if appropriate). Any deviations from the protocol will be reported to the Sponsor as Protocol Deviations.

Administrative changes (not affecting the participant benefit/risk ratio) may be made without the need for a formal amendment. All amendments will be distributed to all protocol recipients, with appropriate instructions.

9 Liability and Insurance

The Sponsor will take out reasonable third-party liability insurance coverage in accordance with all local legal requirements. The civil liability of the Investigator, the persons instructed by him or her and the hospital, practice, or institute in which they are employed and the liability of the Sponsor with respect to financial loss due to personal injury and other damage that may arise as a result of the carrying out of this study are governed by the applicable law.

The Sponsor will arrange for participants participating in this study to be insured against financial loss due to personal injury caused by medical steps taken during the study.

10 Access to Source Data

Regulatory authorities of certain countries, IRBs, and/or the Sponsor's Clinical Quality Assurance Group (or designee) may wish to carry out source data checks and/or on-site audit inspections. Direct access to source data will be required for these inspections and audits; they will be carried out giving due consideration to data protection and medical confidentiality. The Investigator assures the Sponsor and affiliates or designees (such as a CRO) of the necessary for support at all times.

Appendix 2: Adverse Events: Definitions and Procedures for Recording, Evaluating, Follow-up, and Reporting

Definition of AE

AE Definition

• An AE is any untoward medical occurrence in a participant or clinical study participant, temporally associated with the use of a study treatment, whether considered related to the device product.• NOTE: An AE can therefore be any unfavorable and unintended sign, symptom, or disease (new or exacerbated) temporally associated with the use of a study treatment.

Events Meeting the AE Definition

• Any abnormal safety assessments (e.g., vital signs measurements), including those that worsen from baseline, considered clinically significant in the medical and scientific judgment of the Investigator (i.e., not related to progression of underlying disease).• Exacerbation of a chronic or intermittent pre-existing condition includes either an increase in frequency and/or intensity of the condition.• New conditions detected or diagnosed after study treatment administration even though it may have been present before the start of the study.• Signs, symptoms, or the clinical sequelae of a suspected overdose of a concomitant medication. Overdose per se will not be reported as an AE/SAE unless it is an intentional overdose taken with possible suicidal/self-harming intent. Such overdoses should be reported regardless of sequelae.• "Lack of efficacy" or "failure of expected pharmacological action" per se will not be reported as an AE or SAE. Such instances will be captured in the efficacy assessments. However, the signs, symptoms, and/or clinical sequelae resulting from lack of efficacy will be reported as an AE or SAE if they fulfill the definition of an AE or SAE.

Events NOT Meeting the AE Definition

- Any clinically significant abnormal safety assessments which are associated with the underlying disease, unless judged by the Investigator to be more severe than expected for the participant’s condition.
- The disease/disorder being studied or expected progression, signs, or symptoms of the disease/disorder being studied, unless more severe than expected for the participant’s condition.
- Situations in which an untoward medical occurrence did not occur (social and/or convenience admission to a hospital).
- Anticipated day-to-day fluctuations of pre-existing disease(s) or condition(s) present or detected at the start of the study that do not worsen.

Definition of SAE

If an event is not an AE per definition above, then it cannot be an SAE even if serious conditions are met (e.g., hospitalization for signs/symptoms of the disease under study, death due to progression of disease).

An SAE is defined as any untoward medical occurrence that:

Results in death

Is life-threatening

The term 'life-threatening' in the definition of 'serious' refers to an event in which the participant was at risk of death at the time of the event. It does not refer to an event, which hypothetically might have caused death, if it were more severe.

Requires inpatient hospitalization or prolongation of existing hospitalization

In general, hospitalization signifies that the participant has been detained (usually involving at least an overnight stay) at the hospital or emergency ward for observation and/or treatment that would not have been appropriate in the physician’s office or outpatient setting. Complications that occur during hospitalization are AE. If a complication prolongs hospitalization or fulfills any other serious criteria, the event is serious. When in doubt as to whether “hospitalization” occurred or was necessary, the AE should be considered serious.

Results in persistent disability/incapacity

The term disability means a substantial disruption of a person's ability to conduct normal life functions.

This definition is not intended to include experiences of relatively minor medical significance such as uncomplicated headache, nausea, vomiting, diarrhea, influenza, and accidental trauma (e.g., sprained ankle) which may interfere with or prevent everyday life functions but do not constitute a substantial disruption.

Is a congenital anomaly/birth defect

Other situations

Medical or scientific judgment should be exercised in deciding whether SAE reporting is appropriate in other situations such as important medical events that may not be immediately life-threatening or result in death or hospitalization but may jeopardize the participant or may require medical or surgical treatment to prevent one of the other outcomes listed in the above definition. These events should usually be considered serious.

Recording and Follow-up of AE and SAE

AE and SAE Recording

When an AE/SAE occurs, it is the responsibility of the Investigator to review all documentation (e.g., hospital progress notes, laboratory, and diagnostics reports) related to the event.

The Investigator will then record all relevant AE/SAE information in the CRF.

It is **not** acceptable for the Investigator to send photocopies of the participant's medical records in lieu of completion of the AE/SAE CRF page.

There may be instances when copies of medical records for certain cases are requested by the Sponsor. In this case, all participant identifiers, with the exception of the participant number, will be blinded on the copies of the medical records.

The Investigator will attempt to establish a diagnosis of the event based on signs, symptoms, and/or other clinical information. In such cases, the diagnosis (not the individual signs/symptoms) will be documented as the AE/SAE.

Assessment of Intensity

The Investigator will make an assessment of intensity for each AE and SAE reported during the study and assign it to one of the following categories:

Mild: An event that is easily tolerated by the participant, causing minimal discomfort, and not interfering with everyday activities.

Moderate: An event that causes sufficient discomfort and interferes with normal everyday activities.

Severe: An event that prevents normal everyday activities. An AE that is assessed as severe should not be confused with an SAE. Severe is a category utilized for rating the intensity of an event; and both AE and SAE can be assessed as severe.

An event is defined as 'serious' when it meets at least one of the predefined outcomes as described in the definition of an SAE, NOT when it is rated as severe.

Assessment of Causality

The Investigator is obligated to assess the relationship between study treatment and each occurrence of each AE/SAE.

A "reasonable possibility" of a relationship conveys that there are facts, evidence, and/or arguments to suggest a causal relationship, rather than a relationship cannot be ruled out.

The Investigator will use clinical judgment to determine the relationship.

Alternative causes, such as underlying disease(s), concomitant therapy, and other risk factors, as well as the temporal relationship of the event to study treatment administration will be considered and investigated.

The Investigator will also consult the Instruction for Use, in his/her assessment.

For each AE/SAE, the Investigator **must** document in the medical notes that he/she has reviewed the AE/SAE and has provided an assessment of causality.

There may be situations in which an SAE has occurred, and the Investigator has minimal information to include in the initial report to the Sponsor. However, **it is very important that the Investigator always make an assessment of causality for every event before the initial transmission of the SAE data to the Sponsor.**

The Investigator may change his/her opinion of causality in light of follow-up information and send an SAE follow-up report with the updated causality assessment.

The causality assessment is one of the criteria used when determining regulatory reporting requirements.

Follow-up of AE and SAE

The Investigator is obligated to perform or arrange for the conduct of supplemental measurements and/or evaluations as medically indicated or as requested by the Sponsor to elucidate the nature and/or causality of the AE or SAE as fully as possible. This may include laboratory tests or investigations, histopathological examinations, or consultation with other health care professionals.

If a participant dies during participation in the study, the Investigator will provide the Sponsor with a copy of any post-mortem findings including histopathology.

New or updated information will be recorded in the originally completed CRF.

The Investigator will submit any updated SAE data to the Sponsor within 24 hours of receipt of the information.

Reporting of SAE

SAE Reporting

The Investigator must report any SAEs to the Sponsor within 24 hours of becoming aware of the event.

The Investigator and the Sponsor (or Sponsor's designated agent) will review each SAE report and the Sponsor/CRO will evaluate the seriousness and the causal relationship of the event to study treatment. In addition, the Sponsor (or Sponsor's designated agent) will evaluate the expectedness according to the reference documents. Based on the Investigator and Sponsor's assessment of the event, a decision will be made concerning the need for further action.

If a site receives a report of a new SAE from a study participant or receives updated data on a previously reported SAE, report to the Sponsor within 24 h.

Contacts for SAE reporting can be found in the Study Operation Manual.

All SAEs will be recorded from randomization until the end of the study. Serious adverse events occurring after the end of the study and coming to the attention of the Investigator must be reported only if they are considered (in the opinion of the Investigator) causally-related to study treatment.

Suspected Unexpected Serious Adverse Reactions (SUSARs)

Any AE that is serious, associated with the use of the study treatment, and unexpected (SUSAR) has additional reporting requirements, as described below.
 
If the SUSAR is fatal or life-threatening, associated with study treatment, and unexpected, regulatory authorities and IRB will be notified within 7 calendar days after the Sponsor learns of the event. Additional follow-up (cause of death, autopsy report, and hospital report) information should be reported within an additional 8 days (15 days total).
 
If the SUSAR is not fatal or life-threatening but is otherwise serious, associated with study treatment, and unexpected, regulatory authorities and IRBs will be notified within 15 calendar days after the Sponsor learns of the event.

